**(2) Part 2 (multiple-dose study)**

A once-daily oral dose of the study drug will be given to subjects 30 minutes before breakfast. For twice-daily administration, an oral dose of the study drug will be given to subjects 30 minutes before breakfast and before bedtime (12 hours after the dose

before breakfast). (On Day 1 and Day X [day of the last dose], an oral dose of the study drug will be administered 30 minutes before breakfast only.) If effects of diet are predicted by oral administration 30 minutes before breakfast from the results of pharmacokinetics obtained in cohorts S3-1, S3-2 and M1, it is possible to change cohort M2 to oral administration 1 hour or 90 minutes before breakfast, or not to take breakfast after fasting administration only on the administration day.

The dose and duration for Cohorts M1 and M2, and the frequency of administration for Cohort M2 are tentative. Based on the PK and safety data collected in Part 1 and Cohort M1, the sponsor and the medical expert will examine and determine the actual value with the agreement of the investigator. The dose in Cohort M2 should be  $\leq 2/3$  of the highest dose in Part 1. The common ratio between the dose and the estimated mean  $C_{max}$  and  $AUC_{0-24hr}$  should be  $\leq 5$  between successive cohorts.

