### 8.6.3 Meals

- (1) Standard meals will be served to the subjects at fixed times during hospitalization at the study site.
- (2) The subjects will visit the study site without having breakfast on the day of screening, Day -1, and end-of-study assessment. (They are allowed to have breakfast after completing the tests.)
- (3) In Cohorts S1, S2, S3-1, S4, S5, S6, and S7 in Part 1 (single-dose study), the subjects will fast (except for water) from 11:00 p.m. on Day -1, and will receive the study drug without having breakfast on Day 1.
- (4) In Cohort S3-2 in Part 1 (single-dose study), the subjects will fast (except water) from 11:00 p.m. on Day -1. After the completion of tests on Day 1, the subject will have breakfast (high fat diet) and receive the study drug 30 minutes after finishing breakfast. On the day of dosing, the subjects will finish eating breakfast in 15 minutes. The investigator will record the time of starting and finishing breakfast in the CRF.
- (5) For once-daily dosing in Part 2 (multiple-dose study), the subjects will fast (except for water) from 11:00 p.m. on Day -1, and will receive the study drug without taking breakfast. Breakfast should be eaten 30 minutes, 1 hour or 90 minutes after administration, or not eaten. Breakfast on the day of administration will be finished in 15 minutes.
- (6) For twice-daily dosing in Part 2 (multiple-dose study), the subjects will fast (except for water) from 11:00 p.m. on Day -1, and will receive the study drug in the morning and before bedtime (12 hours after the morning dose). Breakfast should be eaten 30 minutes, 1 hour or 90 minutes after administration, or not eaten.

On Day 1 and Day X (day of the last dose), the subjects will receive the study drug in

the morning only. On the day of dosing, the subjects will finish eating breakfast in 15 minutes, and will finish eating supper in 30 minutes. The investigator will record the time of starting supper in the CRF.

- (7) For the safety evaluation, the subjects will fast (except for water) from at least 5 hours before blood sampling.
- (8) From 1 hour before dosing, the subjects will not drink fluids until finishing study drug administration. On Day 1 (all cohorts) and on Day X (day of the last dose) in Part 2 (multiple-dose study), the subjects will not drink fluids up to 2 hours post-dose.

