- 4) Once- or twice-daily administration. For once-daily administration, the study drug will be given in the morning. For twice-daily administration, the study drug will be given in the morning and before bedtime (12 hours after the morning dose). For morning administration under fasting conditions, breakfast will be eaten 30 minutes, 1 hour or 90 minutes after administration, or not eaten.
- 5) Height will be measured at screening only. Body weight will be measured at screening, hospitalization, and end-of-study assessments. BMI will be calculated at screening and hospitalization assessment.
- 6) A physical examination, vital signs (systolic and diastolic blood pressure, pulse rate, and body temperature), and a 12-lead ECG will be assessed at the following time points: screening, at hospitalization, pre-morning dose, 1, 3, 6, and 12 hours post-dose on Days 1 to 5, before breakfast on Days 6 and 7, and end-of-study assessment.
- 7) Sensory tests will be performed at hospitalization assessment and before breakfast on Day 6.
- 8) Laboratory tests (hematology, biochemistry, coagulation test, and urinalysis): The hospitalization assessment will be performed based on results that can be confirmed within the same day. The laboratory tests will be performed at screening, hospitalization assessment, on Days 3 and 6, and end-of-study assessment.
- 9) Blood sampling for drug concentration measurement:
  - Day 1: Prior to administration in the morning (first dose), 15 and 30 minutes post-dose, and 1, 1.5, 2, 4, 6, 8, and 12 hours post-dose
  - Day 2: Prior to administration in the morning (about 24 hours after the first dose)
  - Days 3 and 4: Prior to administration in the morning
  - Day 5: Prior to the last dose (administration in the morning), 15 and 30 minutes post-dose, and 1, 1.5, 2, 4, 6, 8, and 12 hours post-dose
- 10) Day 6: 24 hours after the last dose
- Day 7: 48 hours after the last dose
- 10) Breakfast will be eaten 30 minutes, 1 hour or 90 minutes after administration, or not eaten.

[For 9-day administration]

Study period	Screening		Hospitalization									End-of-study assessment			
	Day	-30 to -2	-1) At hospitalization	1	2	3	4	5	6	7	8	9	10	11	16 (±2)
Time point			Pre-dose	Post-dose											
Hospitalization	Visiting	←	B  × L, S ○ Fasting from 11:00 p.m.	B, L, S  ○ 	○ 	○ 	→ Visiting								
Meals		B  ×													B  ×
Informed consent		X													

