4) Once- or twice-daily administration. For twice-daily administration, the study drug will be given in the morning. For twice-daily administration, the study drug will

be given in the morning and before bedtime (12 hours after the morning dose). For morning administration under fasting conditions, breakfast will be eaten 30 minutes, 1 hour or 90 minutes after administration, or not eaten.

- 5) Height will be measured at screening only. Body weight will be measured at screening, hospitalization, and end-of-study assessments. BMI will be calculated at screening and hospitalization assessment.
- 6) A physical examination, vital signs (systolic and diastolic blood pressure, pulse rate, and body temperature), and a 12-lead ECG will be assessed at the following time points: screening, at hospitalization, pre-morning dose, 1, 3, 6, and 12 hours post-dose on Days 1 to 14, before breakfast on Days 15 and 16, and end-of-study assessment.
- 7) Sensory tests will be performed at hospitalization assessment and before breakfast on Day 15.
- 8) Laboratory tests (hematology, biochemistry, coagulation test, and urinalysis): The hospitalization assessment will be performed based on results that can be confirmed within the same day. The laboratory tests will be performed at screening, hospitalization assessment, on Days 3, 7, 11, and 15, and end-of-study assessment.
- 9) Blood sampling for drug concentration measurement:
  - Day 1: Prior to administration in the morning (first dose), 15 and 30 minutes post-dose, and 1, 1.5, 2, 4, 6, 8, and 12 hours post-dose
  - Day 2: Prior to administration in the morning (about 24 hours after the first dose)
  - Days 3 to 13: Prior to administration in the morning
  - Day 14: Prior to the last dose (administration in the morning), 15 and 30 minutes post-dose, and 1, 1.5, 2, 4, 6, 8, and 12 hours post-dose
  - Day 15: 24 hours after the last dose
  - Day 16: 48 hours after the last dose
- 10) Breakfast will be eaten 30 minutes, 1 hour or 90 minutes after administration, or not eaten.

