#### 9.2.5 Pharmacokinetic Assessments

(1) Volume and time points of blood sampling

The subjects' blood will be drawn at the time points shown in the table below to measure plasma drug concentrations. The investigator (or subinvestigator) will record the date and time of blood sampling in the CRF. The drug concentration measurement laboratory will measure the plasma drug concentrations.

If any other tests are scheduled at the same time point of blood sampling for plasma drug concentration measurement, blood will be drawn at the scheduled time point, and other tests will be performed before or after blood sampling. In principle, a 12-lead ECG and vital signs (except for body temperature) will be measured before blood sampling for plasma drug concentration or safety evaluation.

The acceptable time range for each blood sampling time point will be specified in a separate document.

Part 1 (single-dose study)	Part 2 (multiple-dose study)

• Day 1: Pre-dose, 15 and 30 minutes post-dose, and 1, 1.5, 2, 4, 6, 8, and 12 hours post-dose

	

• Day 1: Pre-dose, 15 and 30 minutes post-dose, and 1, 1.5, 2, 4, 6, 8, and 12 hours post-dose

• Day 2: 24 and 36 hours post-dose

• Day 3: 48 hours post-dose

	

• Day 2: Pre-dose (24 hours after dosing on Day 1)

• Day 3 to Day X -1*: Pre-dose

• Day X*: Pre-dose, 15 and 30 minutes post-dose, and 1, 1.5, 2, 4, 6, 8, and 12 hours post-dose

• Day X + 1*: 24 hours after dosing on Day X*

• Day X + 2*: 48 hours after dosing on Day X*

--	---

\*X = duration (in the case of a 5-day administration, X = 5)

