Descriptive statistics will be calculated for 12-lead ECG data, for each timepoint. Data outside of the reference range will be indicated via an attached flag in the list.

(3) Pharmacokinetics

For the plasma concentrations of unchanged edaravone, sulfate conjugate, and glucuronide conjugate, descriptive statistics will be calculated by dose for each time point and time after dosing. In addition, descriptive statistics will be calculated for the PK parameters (e.g.,  $C_{max}$ ,  $t_{max}$ , AUC, and  $t_{1/2}$ ) of unchanged edaravone, sulfate conjugate, and glucuronide conjugate by dose.

- Dose proportionality will be assessed using the  $C_{max}$ ,  $AUC_{0-\text{last}}$ , and  $AUC_{0-\infty}$  (except for Cohort S3-2) of unchanged edaravone, sulfate conjugate, and glucuronide conjugate collected in Part 1, using a power model. In addition, the linearity will be evaluated using a lack-of-fit test.
- The effect of food on the PK parameters of edaravone will be assessed using the  $C_{max}$ ,  $AUC_{0-\text{last}}$ , and  $AUC_{0-\infty}$  of unchanged edaravone, sulfate conjugate, and glucuronide conjugate in Cohorts S3-1 and S3-2. The geometric mean ratio (fed/fasting conditions) and the 90% confidence interval will be calculated via analysis of variance, using the data after log transformation under fed and fasting conditions and the subjects as factors.
- The ratio of the  $C_{trough}$  (plasma concentration at the end of the dosing interval) of unchanged edaravone, sulfate conjugate, and glucuronide conjugate for each day of dosing to those after the last dose will be calculated for each subject in Part 2, and the geometric mean and 95% confidence interval will also be calculated.
- The linearity factor (LF) will be calculated to assess the linearity of unchanged edaravone, sulfate conjugate, and glucuronide conjugate after multiple doses in Part 2.

$LF = AUC_{0-T} \text{ (last dose)} / AUC_{0-\infty} \text{ (first dose)}$

T: Dosing interval

- The ratio of accumulation (RA) will be calculated to assess the accumulation of unchanged edaravone, sulfate conjugate, and glucuronide conjugate after multiple doses in Part 2.

$RA = AUC_{0-T} \text{ (last dose)} / AUC_{0-T} \text{ (first dose)}$

T: Dosing interval

(4) Pharmacodynamic assessment

For PD assessments, the Statistical Analysis Plan and report will be prepared separately.

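### If Cohort M2 is dosed twice daily, does the trough ratio need a different reference from the value after the last dose?

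*Protocol*

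**What the plan says.** Section 13.4 (3) defines Ctrough as the concentration at the end of the dosing interval and asks for the ratio of this value "for each day of dosing to those after the last dose will be calculated for each subject in Part 2". It states no threshold or decision for the ratio and no separate rule for twice-daily dosing.

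Table 2 in Section 8.3.1 leaves the frequency in M2 open, once or twice daily, to be settled from the data up to Cohorts S6 and M1. Under twice-daily dosing, Section 8.6.3 (6) says subjects "will receive the study drug in the morning and before bedtime (12 hours after the morning dose". The first and last days are exceptions. Section 8.3.1 (2) reads "On Day 1 and Day X [day of the last dose], an oral dose of the study drug will be administered" before breakfast only, so neither day has a bedtime dose.

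Sampling in Section 9.2.5 runs to 12 h on Day 1 and on Day X, the last dosing day, with further samples 24 and 48 h after the last dose. Between those days there is one sample per day: "Day 2: Pre-dose (24 hours after dosing on Day 1"), then morning pre-dose samples. The notes in Section 9.1 (2) agree: "Days 3 and 4: Prior to administration in the morning" in the 5-day schedule and "Days 3 to 13: Prior to administration in the morning" in the 14-day schedule.

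**The concern.** A trough ratio shows approach to steady state most cleanly when all troughs are taken at the same point of the same kind of dosing interval. Once-daily dosing meets this, since every trough is a 24 h value. Twice-daily dosing does not:

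- The reference is an evening sample, 12 h after a fasted morning dose.
- From Day 3 to Day X the troughs are morning samples, 12 h after a bedtime dose on a day when supper is served.
- On Day 2 the sample is 24 h after the single Day 1 dose.

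The protocol treats food as a live matter for M2. Section 8.3.1 (2) opens a provision with "If effects of diet are predicted by oral administration 30 minutes before breakfast", and Section 8.6.3 (6) says the investigator "will record the time of starting supper in the CRF". If evening doses were absorbed differently, a reader who took the daily ratios as approach to a plateau could see a level other than 1 and wrongly conclude that steady state had not been reached.

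**Working it through.** **Schedule check.** The scheduled PK samples for X dosing days are 10 (Day 1) + 1 (Day 2) + (X − 3) + 10 (Day X) + 1 + 1 = X + 20. That gives 25, 29 and 34 for 5, 9 and 14 days, as in Section 9.3. The sampling times are therefore read correctly.

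**Which sample is the reference.** With a 12 h interval, the end of the interval after the last dose is the 12 h sample on Day X. The sample 24 h after the last dose is a whole interval too late. The Day 1 trough is likewise the scheduled 12 h sample, and that one matches the reference fully: both are 12 h after a morning dose.

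**Time since dose.** The bedtime dose comes 12 h after the morning dose, so the next morning's pre-dose sample is 24 − 12 = 12 h after it. From Day 3 to Day X the numerator and the reference agree in elapsed time. Only morning versus bedtime dosing separates them.

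**Size with equal absorption.** Assumptions: one compartment, linear kinetics, X = 5, half-life 6 or 12 h. Let r = 2^(−12/half-life), so r = 0.25 or 0.50, and express concentrations per unit dose.

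- Day 5 pre-dose: r + r² + r³ + r⁴ + r⁵ + r⁶ + r⁸ = 0.33327 or 0.98828.
- 12 h after the last dose: r + r² + … + r⁷ + r⁹ = 0.33332 or 0.99414.
- Day 5 ratio: 1.000 or 0.994.
- Day 1 ratio from its 12 h sample: 0.25/0.33332 = 0.75, or 0.50/0.99414 = 0.50. This is accumulation shown as intended.

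**Size with unequal absorption.** Let evening absorption be f times morning absorption. At steady state the overnight trough is (f·r + r²)/(1 − r²) and the daytime trough is (r + f·r²)/(1 − r²), so their ratio is (f + r)/(1 + f·r). At f = 1 this is 1 for any half-life.

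| Assumed f | Half-life 6 h, steady state | Half-life 12 h, steady state | Day 5 values (6 h, 12 h) |
|---|---|---|---|
| 0.7 | 0.95/1.175 = 0.81 | 1.20/1.35 = 0.89 | 0.81, 0.88 |
| 1.0 | 1.00 | 1.00 | 1.00, 0.99 |
| 1.3 | 1.55/1.325 = 1.17 | 1.80/1.65 = 1.09 | 1.17, 1.09 |

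Over half-lives of 2 to 12 h, more extreme assumptions give Day 5 ratios of 0.51 to 0.80 at f = 0.5 and 1.07 to 1.24 at f = 1.25. The protocol supplies none of these values of f.

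**What another reference would gain.** The alternative is to divide the pre-dose samples by the Day X pre-dose sample. The Day 3 pre-dose value is r + r² + r⁴ = 0.31641 or 0.8125.

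- Against the Day 5 pre-dose sample: 0.949 or 0.822.
- Against the planned 12 h reference: 0.949 or 0.817.

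With equal absorption the two choices tell the same story. In a 5-day cohort the alternative leaves only Days 3 and 4 to compare with Day 5.

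**The case for a change.** The best argument for a change is that Section 13.4 itself fixes the ratio and that better pairing needs no new sample. The pre-dose samples of Days 3 to X − 1 could be set against the Day X pre-dose sample, and the 12 h values after the first and last doses against each other. That series would be nearly unaffected by an evening effect: at f between 0.7 and 1.3 the Day 3 to Day 5 ratio stays at 0.95 (6 h half-life) or between 0.81 and 0.84 (12 h). The abbreviation list also describes Ctrough differently, as the minimum concentration, so the choice of sample could be thought open.

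Some of this stands. The difference in dosing phase is real, and the Day 2 pre-dose sample should not be read as a 12 h trough. The rest is weaker:

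- The explicit definition in Section 13.4, attached to this very ratio, settles the sample.
- The food provisions do not reach the bedtime dose. The fed and fasted comparison uses a high-fat breakfast, and the flexibility in M2 concerns breakfast around the morning dose. The gap between supper and the bedtime dose is not stated, so a fed evening dose is an inference.
- Accumulation and linearity are judged by RA and LF, which compare the last dose with the first. Both are morning doses.
- Section 8.4 describes no cohort transition after M2, so this ratio from M2 steers no later cohort.

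**Conclusion.** No change to the plan is needed. The schedule does produce a difference in dosing phase, but only if M2 is dosed twice daily. M1 and a once-daily M2 are unaffected. Under the protocol's own definition the ratio is about 1 at steady state when morning and evening doses are absorbed alike (1.00 and 0.99 on Day 5 at assumed half-lives of 6 and 12 h). A departure needs an absorption difference that the document does not show, so the range 0.81 to 1.17 is a sensitivity range, not an expected error.

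The ratio is descriptive, and no demonstrated result or conclusion changes with the reference. Sections 13.1 and 13.3 leave detailed procedures and the handling of concentration data to later documents, chiefly the statistical analysis plan. That plan is not shown here and need only be fixed before data lock. If twice-daily dosing is chosen, an analyst can pair the samples sensibly there and list the Day 2 value apart. The sizes rest on linear one-compartment kinetics and on assumed half-lives and evening absorption.

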### 13.5 Changes in the Statistical Analysis Plan

If the statistical analysis plan in this section is changed prior to data lock, both the details of the change and reason will be specified in the Statistical Analysis Plan and Clinical Study Report. If any analytical method is changed or added after data lock, details of the change and reason will be specified in the revised Statistical Analysis Plan and Clinical Study Report, and the results will be divided into those before and after the change or addition.

## **14. Protocol Compliance, Deviations, and Changes**

### **14.1 Agreement to the Protocol and Compliance**

Prior to closing the agreement for the protocol with the sponsor, the investigator must hold a discussion with the sponsor regarding the study based on the protocol, latest investigator's brochure, and other necessary documents that have been provided by the sponsor, and thoroughly examine the ethical and scientific validity of the study.

Based on the results of this examination, the investigator will agree to the protocol with the sponsor. To prove agreement to comply with the protocol, the investigator and the sponsor will sign or affix their name and seal to the clinical study agreement, with the date of agreement.

### **14.2 Protocol Deviations or Changes**

The investigator (or subinvestigator) must not implement any deviation or change to the protocol without prior documented agreement from the sponsor and prior review and documented approval from the IRB, except where necessary to eliminate an immediate hazard to study subjects due to medically unavoidable circumstances.

If it becomes appropriate to revise the protocol based on the details and reasons for a deviation or change, the investigator should submit the revised protocol (draft) to the sponsor, head of the study site, and IRB as promptly as possible, and obtain approval from the IRB and head of the study site, and documented agreement from the sponsor.

The investigator (or subinvestigator) should record all deviations from the protocol. If any deviation from the protocol arises to eliminate an immediate hazard to subjects or due to any other medically unavoidable reason, the investigator should prepare a documented explanation of the reason, submit it to the sponsor and the head of the study site, and retain a copy.

If a change substantially alters the study design or increases the potential risk to the subjects, the investigator will promptly submit a report to the sponsor, head of the study site, and IRB.

## **15. Protocol Revision**

If it becomes necessary to change the protocol during the study period, the sponsor will revise the protocol. The sponsor will determine the content of the change after discussing and obtaining agreement from the investigator. The sponsor will promptly inform the head of the study site regarding the content of the change in writing, and through the head of the study site, the sponsor will obtain approval from the IRB.

If the head of the study site requests a modification of the change based on the view of the IRB, the sponsor will judge the appropriateness of the change and revise the protocol, as necessary. The sponsor will determine the content of the change after discussing and obtaining agreement from the investigator. The sponsor will promptly inform the head of the study site regarding the content of the change in writing, and through the head of the study site, the sponsor will obtain approval from the IRB.

Based on the discussion with the investigator, if it becomes necessary to modify the change, the sponsor will judge the appropriateness of the change and revise the protocol, as necessary. The sponsor will decide on the content of the change after obtaining agreement from the investigator. The sponsor will promptly inform the head of the study site regarding the content of the change in writing, and through the head of the study site, the sponsor will obtain approval from the IRB.

## 16. Termination or Suspension of the Study

### (1) Criteria for termination or suspension of the study

When any of the following conditions occur, the sponsor will determine whether or not the study is to be terminated.

- 1) When new information becomes available that is related to the quality, efficacy, or safety of the study drug, or that is important for the appropriate conduct of the study.
- 2) When a protocol change becomes necessary, but the study site cannot take the necessary action(s).
- 3) When the head of the study site requests for a modification to the protocol based on the view of the IRB, but the sponsor is unable to agree with the modification.
- 4) When the head of the study site requests for termination of the study based on the view of the IRB.
- 5) When the study site conducts any major violation of the GCP, the protocol, or the study contract.

